1 GLOSSARY OF TERMS

Names of Test Product(s)	Throughout this document, test product(s) will be referred to as Alcon serafilcon A contact lenses
Name of Comparator Product(s)	ACUVUE [®] OASYS with HYDRACLEAR [®] PLUS Technology
Adverse Device Effect (ADE)	Adverse event related to the use of an investigational medical device or comparator.
	Note: This definition includes adverse events resulting from insufficient or inadequate instructions for use, deployment, implantation, installation, or operation; any malfunction; and use error or intentional misuse.
Adverse Event (AE)	Untoward medical occurrence, unintended disease or injury, or untoward clinical signs (including abnormal laboratory findings) in subjects, users or other persons, whether or not related to the investigational medical device or comparator and whether anticipated or unanticipated.
	Note: For subjects, this definition includes events related to the investigational medical device, comparator, or the procedures involved. For users or other persons, this definition is restricted to the use of the investigational medical device or comparator.
	Requirements for reporting Adverse Events in the study can be found in Section 11.
Anticipated Serious Adverse Device Effect (ASADE)	An effect which by its nature, incidence, severity, or outcome has been identified in the risk assessment.

Clinical Investigation Plan	The document(s) stating the rationale, objectives, design,
(CIP)	and prespecified analysis, methodology, organization,
	monitoring, conduct, and record-keeping of the clinical
	investigation.
	Note: The protocol and other documents referenced in the
	protocol (for example, the Statistical Analysis Plan, the
	Manual of Procedures, the Deviations and Evaluability
	Plan, and the Protocol Monitoring Plan) comprise the CIP.
Clinical Investigation	The document describing the design, execution, statistical
Report (CIR) / Clinical	analysis, and results of a clinical investigation. The Clinical
Study Report	Investigation Report is synonymous with the Clinical Study
	Report.
	-
Device Deficiency	Inadequacy of a medical device with respect to its identity,
	quality, durability, reliability, usability, safety, or
	performance.
	Note: This definition includes malfunctions use emerge and
	Note: This definition includes malfunctions, use errors, and inadequacy in the information supplied by the manufacturer
	including labelling related to the investigational medical
	device or the comparator.
	Requirements for reporting Device Deficiencies in the study
	can be found in Section 11.
Enrolled Subject	Any subject who signs an informed consent form for
	participation in the study.
Deint of Engell	
Point of Enrollment	The time at which, following recruitment and before any
	clinical investigation-related procedures are undertaken, a
	subject signs and dates the informed consent form.

Interventional Clinical Trial	A pre- or postmarket clinical investigation where the assignment of a subject to a particular medical device is
	decided in advance by a clinical investigation plan, or
	diagnostic or monitoring procedures requested in the CIP are
	in addition to those available as normal clinical practice and
	burden the subject.
Investigational Product	A preventative (vaccine), a therapeutic (drug or biologic),
	device, diagnostic, or palliative used as a test or comparator
	product in a clinical trial, including a product with a
	marketing authorization when used or assembled
	(formulated or packaged) in a way different from the
	authorized form, or when used for an unauthorized
	indication, or when used to gain further information about
	the authorized form.
Malfunction	Failure of an investigational medical device to perform in
	accordance with its intended purpose when used in
	accordance with the instructions for use or clinical
	investigation plan (CIP), or investigator's brochure (IB).
Nonserious Adverse Event	Adverse event that does not meet the criteria for a serious
	adverse event.
Randomized Subject	Any subject who is assigned a randomized treatment.
Serious Adverse Device	Adverse device effect that has resulted in any of the
Effect (SADE)	consequences characteristic of a serious adverse event.

Serious Adverse Event	Adverse event that led to any of the following:
(SAE)	
	• Death.
	• A serious deterioration in the health of the subject, users or other persons as defined by one or more of the following:
	a) a life-threatening illness or injury Note: Life-threatening means that the individual was at immediate risk of death from the event as it occurred, i.e., it does not include an event which hypothetically might have caused death had it occurred in a more severe form.
	 b) any potentially sight-threatening event or permanent impairment to a body structure or a body function including chronic diseases.
	c) inpatient hospitalization or prolonged hospitalization.
	d) a medical or surgical intervention to prevent a) or b).
	e) any indirect harm as a consequence of incorrect diagnostic test results when used within manufacturer's instructions for use.
	• Fetal distress, fetal death, congenital abnormality or birth defect including physical or mental impairment.
	Note: Planned hospitalization for a preexisting condition, or a procedure required by the CIP, without serious
	deterioration in health, is not considered a serious adverse event.
	Refer to Section 11 for additional SAEs.

Serious Health Threat	 Signal from any adverse event or device deficiency that indicates an imminent risk of death or a serious deterioration in the health in subjects, users, or other persons, and that requires prompt remedial action for other subjects, users, or other persons. Note: This would include events that are of significant and unexpected nature such that they become alarming as a potential serious health hazard or possibility of multiple deaths occurring at short intervals.
Significant Nonserious Adverse Event	 A significant non-serious adverse event is a symptomatic, device-related, non-sight-threatening adverse event that warrants discontinuation of any contact lens wear for greater than or equal to 2 weeks. Refer to Section 11 for additional Significant Nonserious AEs.
Study Start	The start of the study is considered to coincide with the enrollment of the first patient.
Study Completion	The completion of the study is considered to coincide with the study-level last subject last visit or the decision to terminate the trial, whichever is later.
Unanticipated Serious Adverse Device Effect (USADE)	Serious adverse device effect which by its nature, incidence, severity, or outcome has not been identified in the risk assessment.

Use Error	User action or lack of user action while using the medical
	device that leads to a different result than that intended by
	the manufacturer or expected by the user.
	Note:
	a) Use error includes the inability of the user to complete a task.
	b) Use errors can result from a mismatch between the characteristics of the user, user interface, task, or use environment.
	c) Users might be aware or unaware that a use error has occurred.
	d) An unexpected physiological response of the patient is not by itself considered a use error.
	e) A malfunction of a medical device that causes an unexpected result is not considered a use error."

2 LIST OF ACRONYMS AND ABBREVIATIONS

[figure not shown]
Abbreviation	Definition
ADE	Adverse device effect
AE	Adverse event
AOHP	ACUVUE [®] OASYS with HYDRACLEAR [®] PLUS Technology
ASADE	Anticipated serious adverse device effect
BCVA	Best corrected visual acuity
CFR	Code of Federal Regulations
CIP	Clinical investigation plan
CIR	Clinical investigation report
COL	Clinical Operations Lead
CRF	Case report form
CSM	Clinical Site Manager
CTT	Clinical Trial Team
D	Diopter
DEP	Deviations and evaluability plan
Diff	difference
eCRF	Electronic case report form
EDC	Electronic data capture
EN	European Standard
FAS	Full analysis set
FDA	Food and Drug Administration
GCP	Good Clinical Practice
IB	Investigator's brochure
ICF	Informed consent form
IEC	Independent ethics committee
IP	Investigational product
IRB	Institutional review board
ISO	International Organization for Standardization
LogMAR	Logarithm of the minimum angle of resolution
mm	millimeter
MOP	Manual of procedures
N	Number of subjects
N/A	Not applicable
NI	Noninferiority
OD	Right eye
OS	Left eye
OU	Both eyes
РР	Per Protocol
SADE	Serious adverse device effect
SAE	Serious adverse event

[figure not shown]
Abbreviation	Definition
SD	Standard deviation
Seq	sequence
SLE	Slit lamp examination
SOP	Standard operating procedure
UCL	Upper confidence limit
US	United States
USADE	Unanticipated serious adverse device effect
VA	Visual acuity

3 PROTOCOL SUMMARY

Investigational	Device
product type	
F	
Study type	Interventional
	$T \rightarrow D \rightarrow A \rightarrow A$
Investigational	Test Product: Alcon serafilcon A contact lenses (LID022821)
products	Comparator Product: ACUVUE [®] OASYS with HYDRACLEAR [®]
	PLUS Technology contact lenses
Purpose and	The purpose of this study is to assess the clinical performance of the
Scientific	investigational Alcon serafilcon A contact lenses as compared to
Rationale for	marketed ACUVUE [®] OASYS with HYDRACLEAR [®] PLUS
the Study	Technology contact lenses when worn on a daily wear modality.
	The design of this study is
	justified based upon preclinical and clinical testing, as described within
	the investigator's brochure. AOHP contact lenses were chosen as the
	comparator product because these lenses also are reusable contact lenses
	(see Package Insert for AOHP contact lenses). Subjects will be provided
	with CLEARCARE [®] Cleaning & Disinfecting Solution to use with the
	study lenses.
	-

Brief	This study aims to compare the clinical performance
Summary of	at the end of the
the Protocol	replacement cycles of Alcon serafilcon A contact lenses compared to ACUVUE [®] OASYS with HYDRACLEAR [®] PLUS Technology contact lenses, when worn on a daily wear modality. Volunteer subjects aged 18 or over who are habitual spherical soft contact lens wearers (excluding current/previous AOHP habitual lens wearers and daily disposable lens wearers), have at least 3 months of contact lens wearing experience, and who wear their habitual lenses at least 5 days per week and at least 8 hours per day, will be included. This is a prospective, randomized, double-masked, bilateral, crossover study. The expected outcome of this study is to demonstrate noninferiority in the visual acuity at distance when wearing Alcon serafilcon A contact lenses compared to AOHP contact lenses
Objective(s)	 The primary objective of this study is to demonstrate noninferiority in the visual acuity at distance when wearing Alcon serafilcon A contact lenses compared to ACUVUE[®] OASYS with HYDRACLEAR[®] PLUS Technology contact lenses when worn on a daily wear modality.
	• The safety objective is to describe the safety profile of the study products.
Endpoint(s)	Primary EfficacyDistance visual acuity (logMAR) with study lenses at Week 1

	Safety
	• Adverse events
	Biomicroscopy findings
	Device deficiencies
Assessment(s	B) Effectiveness
	• BCVA (logMAR distance with manifest refraction)
	Manifest refraction
	• Distance visual acuity (logMAR) with study lenses
	Safety
	Adverse events
	 Biomicroscopy
	 Device deficiencies

Study Design	This will be a multisite, prospective, randomized, double masked, bilateral, crossover study comparing 2 reusable soft contact lenses. The expected duration of subject participation in the study is approximately 28 days (~14 days per each lens type), with 7 scheduled visits. Subjects will be asked to wear their habitual spectacles only (no contact lens wear) during the washout periods for 2 (at least 48 hours) to 4 days after Visit 1 and after Visit 4.
Subject	Planned number of subjects enrolled/consented: ~185
population	Planned number of completed subjects: 168
Sites and	Planned number of clinical sites: ~ 14
Locations	Planned locations (initial list of locations, which may change during start up or conduct according to study needs): US
Key inclusion criteria (See Section 8.1 for a complete list of inclusion criteria)	 Successful wear of spherical soft contact lenses in both eyes for a minimum of 5 days per week and 8 hours per day during the past 3 months. Manifest cylinder of ≤ -0.75 D in each eye. Best corrected visual acuity (BCVA) 20/25 Snellen (0.10 logMAR) or better in each eye.
Key exclusion criteria (See Section 8.2 for a complete list of exclusion criteria)	 Wearing habitual contact lenses in an extended wear modality (routinely sleeping in lenses for at least 1 night per week) over the last 3 months prior to enrollment. Habitual AOHP contact lens wearers and current habitual wearers of any daily disposable contact lenses.
Data analysis and sample size justification	Planned Data Analysis

Endpoint	Comparison	Statistical Model	
Primary	Comparison	Statistical Work	
Distance VA	Alcon serafilcon A contact lenses vs AOHP contact lenses	Mixed effects repeated measures NI margin = 0.05 (logMAR)	
Sample Size Ju Sample size cal	istification culation is based on a	prior clinical study	
which evaluated AOHP contact		on serafilcon A contact lenses and	

Associated materials	• CLEARCARE [®] Cleaning & Disinfecting Solution supplied by sponsor to be provided to subjects for use during the study.
	• Lubrication/rewetting drops will not be permitted.
	• CLEARCARE [®] Plus with Hydraglyde Cleaning & Disinfecting Solution is not recommended.

Table 3–1 Schedule of Study Procedures and Assessment

			Len				Lens 2			
Procedure/ Assessment	Pres cree ning	Visit 1 Screening / Baseline	(Perio Visit 2 Dispense Lens 1 [2 (at least 48 hours) – 4 days after Visit 1 (Washout period with habitual spectacles only after Visit 1)]	od 1) Visit 3 Week 1 Follow-up Lens 1 [7 -0/+ 1 days after Visit 2]	Visit 4 Week 2 Follow- up Lens 1 [7 -0/+ 1 days after Visit 3)]	Visit 5 Dispense Lens 2 [2 (at least 48 hours) – 4 days after Visit 4 (Washout period with habitual spectacles only after Visit 4)]	(Period 2) Visit 6 Week 1 Follow-up Lens 2 [7 -0/+ 1 days after Visit 5]	Visit 7 Week 2 Follow-up Lens 2 /Exit [7 -0/+ 1 days after Visit 6)]	Early Exit	Unsche duled Visit
Informed Consent		Х	VISIT I)			visit 4)				
Demographics		X								
Medical History		Х	Х	Х	Х	Х	Х	Х	Х	X
Concomitant Medications		Х	Х	Х	х	Х	Х	Х	Х	X
Inclusion/ Exclusion		Х								
Habitual lens (brand, lens power, lens care)		Х								
In office subjective questionnaire • Habitual lens wear and rewetting drop usage		Х								
17 4 4		X.								
Keratometry		Х	(X)	(X)	(X)	(X)	(X)	(X)	(X)	(X)

			Len (Peri				Lens 2 (Period 2)			
Procedure/ Assessment	Pres cree ning	Visit 1 Screening / Baseline	Visit 2 Dispense Lens 1 [2 (at least 48 hours) – 4 days after Visit 1 (Washout period with habitual spectacles only after Visit 1)]	Visit 3 Week 1 Follow-up Lens 1 [7 -0/+ 1 days after Visit 2]	Visit 4 Week 2 Follow- up Lens 1 [7 -0/+ 1 days after Visit 3)]	Visit 5 Dispense Lens 2 [2 (at least 48 hours) – 4 days after Visit 4 (Washout period with habitual spectacles only after Visit 4)]	Visit 6 Week 1 Follow-up Lens 2 [7 -0/+ 1 days after Visit 5]	Visit 7 Week 2 Follow-up Lens 2 /Exit [7 -0/+ 1 days after Visit 6)]	Early Exit	Unsche duled Visit
VA w/ habitual correction ⁺ (OD, OS, logMAR distance)*		х						Х	х	(X)
Manifest refraction*		Х	(X)	(X)	(X)	(X)	(X)	(X)	(X)	(X)
BCVA (OD, OS, logMAR distance with manifest refraction)		х	(X)	(X)	(X)	(X)	(X)	(X)	(X)	(X)
Biomicroscopy		Х	Х	Х	Х	Х	Х	Х	Х	Х

			Len (Peri				Lens 2 (Period 2)			
Procedure/ Assessment	Pres cree ning	Visit 1 Screening / Baseline	Visit 2 Dispense Lens 1 [2 (at least 48 hours) – 4 days after Visit 1 (Washout period with habitual spectacles only after Visit 1)]	Visit 3 Week 1 Follow-up Lens 1 [7 -0/+ 1 days after Visit 2]	Visit 4 Week 2 Follow- up Lens 1 [7 -0/+ 1 days after Visit 3)]	Visit 5 Dispense Lens 2 [2 (at least 48 hours) – 4 days after Visit 4 (Washout period with habitual spectacles only after Visit 4)]	Visit 6 Week 1 Follow-up Lens 2 [7 -0/+ 1 days after Visit 5]	Visit 7 Week 2 Follow-up Lens 2 /Exit [7 -0/+ 1 days after Visit 6)]	Early Exit	Unsche duled Visit
Fitting of investigational products (trial assessments): (Test and Comparator)* - VA (logMAR distance) - Lens movement (Overall fit- primary and peripheral gazes) - Lens position (Centration)		Х								
Randomization		Х								
Dispense study lenses			X	X	V	X	X	v		(X)
VA w/study lenses, (OD, OS, logMAR			Х	Х	Х	Х	Х	Х	(X)	(X)

			Ler (Peri				Lens 2 (Period 2)			
Procedure/ Assessment	Pres cree ning	Visit 1 Screening / Baseline	Visit 2 Dispense Lens 1 [2 (at least 48 hours) – 4 days after Visit 1 (Washout period with habitual spectacles only after	Visit 3 Week 1 Follow-up Lens 1 [7 -0/+ 1 days after Visit 2]	Visit 4 Week 2 Follow- up Lens 1 [7 -0/+ 1 days after Visit 3)]	Visit 5 Dispense Lens 2 [2 (at least 48 hours) – 4 days after Visit 4 (Washout period with habitual spectacles only after	Visit 6 Week 1 Follow-up Lens 2 [7 -0/+ 1 days after Visit 5]	Visit 7 Week 2 Follow-up Lens 2 /Exit [7 -0/+ 1 days after Visit 6)]	Early Exit	Unsche duled Visit
			spectacles			spectacles				

			Len (Peri	od 1)			Lens 2 (Period 2)			
Procedure/ Assessment	Pres cree ning	Visit 1 Screening / Baseline	Visit 2 Dispense Lens 1 [2 (at least 48 hours) – 4 days after Visit 1 (Washout period with habitual spectacles only after	Visit 3 Week 1 Follow-up Lens 1 [7 -0/+ 1 days after Visit 2]	Visit 4 Week 2 Follow- up Lens 1 [7 -0/+ 1 days after Visit 3)]	Visit 5 Dispense Lens 2 [2 (at least 48 hours) – 4 days after Visit 4 (Washout period with habitual spectacles only after	Visit 6 Week 1 Follow-up Lens 2 [7 -0/+ 1 days after Visit 5]	Visit 7 Week 2 Follow-up Lens 2 /Exit [7 -0/+ 1 days after Visit 6)]	Early Exit	Unsche duled Visit
AEs ^α		Х	Х	Х	Х	Х	Х	Х	Х	Х
Device deficiencies		X	X	X	X	X	X	X	X	X
Exit Form		(X)	(X)	(X)	(X)	(X)	(X)	Х	Х	(X)

(X) Assessment performed as necessary, e.g., decrease of VA by 2 lines or more with investigational product (IP)

* Source only (source transferred to the sponsor upon request)

α Comprehensive details of all AEs will be documented in the source records, however limited collection will be utilized in the eCRF (see MOP for details).

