10.2.4 Adverse Event Collection: Safety Assessment

Assess and record any adverse events that are observed or reported since the previous visit, including those associated with changes in concomitant medication dosing in the subject source documents. See Section 11 for further details regarding AE collection and reporting.

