10.3 Unscheduled Visits

If a subject visit occurs between any regularly scheduled visit and the visit is conducted by study personnel, this visit must be documented as an unscheduled visit. If the subject seeks medical attention outside the clinic (for example, at an emergency room) or at the clinic but is seen by non-study personnel, the investigator is to capture adverse event-related information on the Adverse Event form upon becoming aware.

During all unscheduled visits, the investigator must conduct the following procedures:

- Collect adverse event information
- Collect Device Deficiency information
- Record changes in medical condition or concomitant medication
- Biomicroscopy
- Review lens wear calendar

The investigator may perform additional procedures for proper diagnosis and treatment of the subject. The investigator must document this information in the subject's case history source documents.

If during an unscheduled visit the subject is discontinuing the IP or discontinuing from the study, the investigator must conduct Exit procedures according to Table 3-1 Schedule of Study Procedures and Assessments and Section 10.4.3, as possible.

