11.3 Procedures for Recording and Reporting

AEs are collected from the time of informed consent. Any preexisting medical conditions or signs/symptoms present in a subject prior to the start of the study (i.e., before informed consent is signed) are not considered AEs in the study and should be recorded in the Medical History section of the eCRF.

For each recorded event, the ADEs and SAEs documentation must include date of occurrence, severity, treatment (if applicable), outcome, and assessments of the seriousness and causality. Furthermore, the investigator must document all device deficiencies reported or observed with test and control products on the Device Deficiency eCRF. The site must submit all available information on ADEs, SAEs, and device deficiencies to the study sponsor immediately as follows:

- ADEs or SAEs are documented on the *Serious Adverse Event and Adverse Device Effect* eCRF within 24 hours of the investigator's or site's awareness.
- Device deficiencies are documented on the *Device Deficiency* eCRF within 24 hours of the investigator's or site's awareness.
- A printed copy of the completed *Serious Adverse Event and Adverse Device Effect* and/or *Device Deficiency* eCRF must be included with product returns.
- Additional relevant information after initial reporting must be entered into the eCRF as soon as the data become available.
- Document any changes to concomitant medications on the appropriate source form.
- Document all relevant information from Discharge Summary, Autopsy Report,
- Certificate of Death etc., if applicable, in narrative section of the *Serious Adverse Event and Adverse Device Effect* eCRF.

Note: Should the EDC system become non-operational, the site must complete the appropriate paper *Serious Adverse Event and Adverse Device Effect* and/or *Device Deficiency* Form. The completed form is emailed to the Study Sponsor at [contact] according to the timelines outlined above; however, the reported information must be entered into the EDC system once it becomes operational.

In addition to recording all AEs into the EDC system, any AEs and device deficiencies for non-study marketed devices/products (e.g., CLEAR CARE[®] Cleaning & Disinfecting Solution used concomitantly during the study will be considered and processed as spontaneous following the postmarket vigilance procedures) and should be communicated to the device's/product's manufacturer as per local requirements.

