12.2 Analysis Sets

12.2.1 Safety Analysis Set

Safety analyses will be conducted using the safety analysis set on a treatment-emergent basis. As such, the safety analysis set will include all subjects/eyes exposed to any study lenses evaluated in this study,

. For treatment-

emergent safety analyses, subjects/eyes will be categorized under the actual study lenses exposed in the corresponding lens sequence.

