12.6 Safety Analyses

The safety endpoints are:

- AEs
- Biomicroscopy findings
- Device Deficiencies

There are no safety hypotheses planned in this study. The focus of the safety analysis will be a comprehensive descriptive assessment of occurrence of adverse events as well as the other listed parameters.

All AEs occurring from the time a subject signs informed consent to study exit will be accounted for in the reporting. Safety analyses will be conducted using the safety analysis set on a treatment-emergent basis. Descriptive summaries (frequencies and percentages) for ocular and nonocular AEs will be presented by Medical Dictionary for Regulatory Activities Preferred Terms. AEs leading to study discontinuation and SAEs will be identified. Individual subject listings will be provided, as necessary.

Individual subject listings will be provided for AEs that occur after signing informed consent but prior to exposure to IP.

Each biomicroscopy parameter will be tabulated by its grade. For each biomicroscopy parameter, counts and percentages of eyes that experience an increase of ≥ 2 grades from baseline (last assessment prior to study lens exposure) to any subsequent visit within the same period will be presented. A supportive listing will be generated which will include all biomicroscopy data from all visits within the same period for those eyes experiencing the increase.

Two listings for device deficiencies, prior to exposure to study contact lenses and treatmentemergent, will be provided. Additionally, each device deficiency category will be tabulated. No inferential testing will be conducted for the safety analyses.

[figure not shown]

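### Does limited collection of adverse events in the eCRF leave the Section 12.6 safety tables without the events or the timing they need?

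*Protocol*

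**What the plan says.** The AE footnote to Table 3-1 (Section 3) puts comprehensive detail on all AEs in source records and then says "however limited collection will be utilized in the eCRF (see MOP for details". Section 10.2.4 has AEs since the previous visit assessed and recorded, "including those associated with changes in concomitant medication dosing in the subject source documents", and refers to Section 11 for collection and reporting.

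Section 11.3 gives the itemised content rule: "For each recorded event, the ADEs and SAEs documentation must include date of occurrence, severity", followed by treatment, outcome, seriousness and causality. Later in the same section, a paragraph on non-study marketed products opens "In addition to recording all AEs into the EDC system". For events handled away from study staff, Section 10.3 says "the investigator is to capture adverse event-related information on the Adverse Event form upon becoming aware".

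On the analysis side, Section 12.6 states "All AEs occurring from the time a subject signs informed consent to study exit will be accounted for in the reporting". It works on a treatment-emergent basis and adds "Individual subject listings will be provided for AEs that occur after signing informed consent but prior to exposure to IP". Section 12.2.1 says that "subjects/eyes will be categorized under the actual study lenses exposed in the corresponding lens sequence".

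**The concern.** Taken alone, the footnote can be read in two ways: a short record for every event, or a record only for some events. Section 10.2.4 mentions source documents only, and the only AE form that Section 11.3 names is the one for SAEs and ADEs. A site could infer that a non-serious, unrelated AE need not reach the database. The tables in Section 12.6 would then cover fewer events than they claim to.

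Even if every event is entered, the visible text nowhere expressly requires an onset date in the eCRF for a non-serious, unrelated AE. In a two-period crossover, timing decides whether an event is listed as pre-exposure, counted under the first lens or counted under the second. An SAP cannot recover timing that was never captured. At stake would be the completeness and lens attribution of the descriptive AE tables, not the visual acuity comparison.

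**Working it through.** No sample size, margin or error rate is involved, so the check is mainly a comparison of sections.

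**Step 1: fewer events or fewer fields?**

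| Place in the protocol | What it implies |
|---|---|
| Table 3-1 footnote | Limited collection, unspecified; details in the MOP |
| 10.3 | An Adverse Event form exists and is used for events seen outside the study team |
| 11.1 | Reporting covers serious and non-serious AEs |
| 11.3 | Recording of all AEs in the EDC system is taken as given |
| 11.3, causality text | Causality is judged for every AE; the sponsor may upgrade unrelated to related and non-serious to serious |
| 11.6 | Follow-up of AEs ongoing at discontinuation goes into the eCRFs |
| 12.6 | All AEs from consent to exit are accounted for |

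The fewer-events reading conflicts with Sections 11.3 and 12.6. It would also make the sponsor's power to upgrade hard to use, because unrelated, non-serious events would not reach the sponsor. The fewer-fields reading fits every row.

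**Step 2: which fields are secured for other AEs?** Section 11.3 lists six items for ADEs and SAEs: date, severity, treatment, outcome, seriousness and causality. For AEs in general, two are explicit: causality, and intensity where appropriate. Seriousness is presupposed, since the sponsor can upgrade the investigator's assessment of it. Outcome is partly covered by Section 11.6. Date is not stated. The footnote sends this level of detail to the MOP, just as Section 10.2.2 does for medical history and concomitant medications.

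**Step 3: does the schedule supply the timing?** Table 3-1 has AEs assessed at Visits 1 to 7 and at early exit and unscheduled visits. By Section 10.2.4 each assessment covers the time since the previous visit. The visit table in Section 10 then gives:

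| AE recorded at | Interval covered | State |
|---|---|---|
| Visit 2 | Visit 1 to 2 | First washout, before dispensing |
| Visits 3 and 4 | Visit 2 to 4 | Lens 1 |
| Visit 5 | Visit 4 to 5 | Second washout |
| Visits 6 and 7 | Visit 5 to 7 | Lens 2 |

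Each boundary that the safety analysis needs falls on a scheduled visit. The visit at which an event is first recorded therefore ordinarily gives the period without a calendar date.

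**Step 4: how much time lies off-lens?** From the visit windows:

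- Washout: 2 × (2 to 4) = 4 to 8 days.
- Wear: 2 × [(7 to 8) + (7 to 8)] = 28 to 32 days.
- Total: 32 to 40 days.
- Lowest washout share: 4 / (4 + 32) = 11.1%.
- Highest washout share: 8 / (8 + 28) = 22.2%.

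These are shares of calendar days. They are not shares of AEs at risk of misplacement, because each washout is closed at both ends by a visit at which AEs are collected.

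**The case for a change.** The strongest reply is that the protocol should secure the minimum data its own analysis requires. The clause about recording all AEs in the EDC is a subordinate clause in a paragraph about other products, not a stand-alone instruction. The only explicit date rule stops at ADEs and SAEs. The MOP is not available here, so reliance on it cannot be verified. Visit intervals can also fail: an event that began in washout may first be mentioned at a later visit.

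Some of this stands. The footnote does not define its own term, and no visible passage expressly requires a date or visit interval in the eCRF for non-serious, unrelated AEs. But that is silence about a field, deferred by name to a controlled study document. It is not a rule that produces a wrong table. The date requirement in Section 11.3 sits with the 24-hour reporting rules for ADEs and SAEs and does not say that other events go undated. A late-mentioned event can be queried against source, where full detail is kept. How an event starting in the second washout is assigned to a lens is a separate convention, commonly left to the SAP, and an onset date alone would not settle it.

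**Conclusion.** No change to the plan is needed. The protocol taken as a whole means that every AE is entered, with fewer fields per event. The remaining gap is the field list for non-serious, unrelated AEs, which the MOP and the database build would be expected to fill.

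The demonstrated effect is nil: no AE is shown to be lost or placed under the wrong lens. The tables concerned are descriptive, with no safety hypotheses and no inferential testing, and the Week 1 visual acuity comparison does not use these data.

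This rests on three assumptions:

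- The MOP's field set includes an onset date, or the eCRF ties each AE to a visit.
- Sites follow Section 10.2.4 and ask about AEs at each visit.
- Trial fitting at Visit 1 does not count as exposure for the pre-exposure listing. The safety set definition in Section 12.2.1 is incomplete in the public copy, so this cannot be confirmed.

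If the text is reopened for another reason, the sponsor could add to the footnote that every AE is entered with at least term, onset date or visit interval, seriousness and relatedness, with a cross-reference to Section 11.3. That would record what is already implied and would change no result or conclusion.
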